**Procedures of Visit 1 (Day 1 of Week 0)**

- Physical examination.
- Blood sampling for immunogenicity study (must be done BEFORE the injection of BCD-085/placebo) [REDACTED]
- Complete blood count [REDACTED]
- Blood chemistry [REDACTED]
- Information about concomitant therapy.
- Administration of BCD-085/placebo.
- Blood pressure, wrist pulse, and body temperature are measured any time before and immediately after the administration of the investigational product.
- Assessing injection site reactions (two times): 4 h and 8 h after the injection of BCD-085/placebo.
- Recording AEs/SAEs.

**Procedures of Visit 2 (Day 1 of Week 1), performed 7 days after the first injection of BCD-085/placebo**

- Physical examination.
- The patient fills out the VAS for itch.
- Administration of BCD-085/placebo.
- Blood pressure, heart rate and body temperature (immediately after dosing).
- Information about concomitant therapy.
- Assessing injection site reactions.
- Recording AEs/SAEs.

**Procedures of Visit 3 (Day 1 of Week 2)**

- Physical examination.
- Administration of BCD-085/placebo.
- Blood pressure, heart rate and body temperature (immediately after dosing).
- Information about concomitant therapy.
- Assessing injection site reactions.

- Recording AEs/SAEs.

### **Procedures of Visit 4 (Day 1 of Week 4)**

- Physical examination.
- Administration of BCD-085/placebo.
- Blood pressure, heart rate and body temperature (immediately after dosing).
- Information about concomitant therapy.
- Assessing injection site reactions.
- Recording AEs/SAEs.

### **Procedures of Visit 5 (Day 1 of Week 6)**

- Physical examination.
- Administration of BCD-085/placebo.
- Blood pressure, heart rate and body temperature (immediately after dosing).
- Information about concomitant therapy.
- Assessing injection site reactions.
- Recording AEs/SAEs.

### **Procedures of Visit 6 (Day 1 of Week 8)**

- Physical examination.
- Psoriasis Area and Severity Index (PASI), including Body Surface Area affected by psoriasis (BSA).
- Static Physician's Global Assessment (sPGA).
- [REDACTED]
- DLQI questionnaire.
- Administration of BCD-085/placebo.
- Blood pressure, heart rate and body temperature (immediately after dosing).
- Complete blood count [REDACTED]
- Blood chemistry [REDACTED]
- Urinalysis.
- Information about concomitant therapy.
- Assessing injection site reactions.

- Recording AEs/SAEs.

### **Procedures of Visit 7 (Day 1 of Week 10)**

- Physical examination.
- Administration of BCD-085/placebo.
- Blood pressure, heart rate and body temperature (immediately after dosing).
- Information about concomitant therapy.
- Assessing injection site reactions.
- Recording AEs/SAEs.

### **Procedures of Visit 8 (Day 1 of Week 12)**

- Information about concomitant therapy.
- Physical examination.
- Psoriasis Area and Severity Index (PASI), including Body Surface Area affected by psoriasis (BSA).
- Static Physician's Global Assessment (sPGA).
- [REDACTED]
- The patient fills out the VAS for itch.
- DLQI questionnaire.
- Nail Psoriasis Severity Index (NAPSI).
- Assessment of psoriatic arthritis: swollen/tender joint count(66/68), VAS by the patient (pain, disease activity) and by the physician (disease activity), functional activity with HAQ-DI.
- Unblinding.
- Taking a blood sample for immunogenicity assay [REDACTED]
- Complete blood count [REDACTED]
- Blood chemistry [REDACTED]
- hs-CRP, atherogenicity index, apoB1/apoA1 [REDACTED]
- Urinalysis.

Translated from Russian to English, dated 26-Nov-2019

- Administration of BCD-085 (only to patients from Arm 3: first administration of BCD-085).
- Blood pressure, heart rate and body temperature (immediately after dosing).
- ECG.
- Assessing injection site reactions.
- Recording AEs/SAEs.

#### **Procedures of Visit 8-1 (Day 1 of Week 13) (only in patients from Arm 3)**

- Physical examination.
- Information about concomitant therapy.
- Second administration of BCD-085.
- Blood pressure, heart rate and body temperature (immediately after dosing).
- Assessing injection site reactions.
- Recording AEs/SAEs.

#### **Procedures of Visit 9 (Day 1 of Week 14)**

- Physical examination.
- Information about concomitant therapy.
- Administration of BCD-085.
- Blood pressure, heart rate and body temperature (immediately after dosing).
- Assessing injection site reactions.
- Recording AEs/SAEs.

#### **Procedures of Visit 10 (Day 1 of Week 16)**

- Information about concomitant therapy.
- Psoriasis Area and Severity Index (PASI), including Body Surface Area affected by psoriasis (BSA).
- Static Physician's Global Assessment (sPGA).

 For patients of Arm 3 just after the administration of the investigational product.

 In Arm 3, assessment of injection site reactions on Visit 8 (Week 12) is performed 4 h and 8 h after the injection of BCD-085.

- Recording AEs/SAEs.

### **Procedures of Visit 11 (Day 1 of Week 18)**

- Physical examination.
- Information about concomitant therapy.
- Administration of BCD-085.
- Blood pressure, heart rate and body temperature (immediately after dosing).
- Assessing injection site reactions.
- Recording AEs/SAEs.

### **Procedures of Visit 12 (Day 1 of Week 22)**

- Physical examination.
- Information about concomitant therapy.
- Administration of BCD-085.
- Blood pressure, heart rate and body temperature (immediately after dosing).
- Assessing injection site reactions.
- Recording AEs/SAEs.

### **Procedures of Visit 13 (Day 1 of Week 24)**

- Information about concomitant therapy.
- Taking a blood sample for immunogenicity assay [REDACTED]
- hs-CRP, atherogenicity index, apoB1/apoA1 [REDACTED]
- Psoriasis Area and Severity Index (PASI), including Body Surface Area affected by psoriasis (BSA).
- Static Physician's Global Assessment (sPGA).
- Nail Psoriasis Severity Index (NAPSI).
- [REDACTED]
- The patient fills out the VAS for itch.
- DLQI questionnaire.
- Complete blood count [REDACTED]
- Blood chemistry [REDACTED]
- Urinalysis.

- Assessing psoriatic arthritis: swollen/tender joint count (66/68), VAS by the patient (pain, disease activity) and by the physician (disease activity), functional activity with HAQ-DI.
- Recording AEs/SAEs.

### Procedures of Visit 14 (Day 1 of Week 26)

- Physical examination (including body weight).
- TB test [REDACTED]  
[REDACTED]  
[REDACTED]
- Administration of BCD-085.
- Blood pressure, heart rate and body temperature (immediately after dosing).
- ECG.
- Information about concomitant therapy.
- Assessing injection site reactions.
- Recording AEs/SAEs.

### Procedures of Visit 15 (Day 1 of Week 30)

- Physical examination.
- Information about concomitant therapy.
- Administration of BCD-085.
- Blood pressure, heart rate and body temperature (immediately after dosing).
- Assessing injection site reactions.
- Recording AEs/SAEs.

---

If the patient has to take a Diaskintest, he/she will receive a referral for the test on this Visit. The Diaskintest must be performed within 7 days after the referral. If the TB test show uncertain/positive results, the patient should be called to the study site for an unscheduled visit where he/she will be given a referral to a TB clinic. If the TB is confirmed, this must be registered as an AE, and the patient must be withdrawn from the study. Patients can continue the study if the TB Specialist provides a documented impression that the patient has no TB infection (the blood work for TB may be repeated on the discretion of the TB Specialist).

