Instrumental examinations	• 12-lead ECG	×6: 1. Screening 2. Day 1 of Week 12 3. Day 1 of Week 26 4. Day 1 of Week 54 5. Day 1 of Week 110 6. Day 1 of Week 158 (only for patients from Arms 1 and 2) 7. Day 1 of Week 170 (only for Arm 3)	Study site/third-party contractors
	• Chest X-ray. 	×6: 1. At screening 2. Day 1 of Week 54 3. Day 1 of Week 86  4. Day 1 of Week 110 	Study site/third-party contractors

 Pregnancy test detecting hCG in the urine (test strips). Pregnancy test is not required if the female patient is at least 2 years post-menopausal or had a uterus or ovary surgery that makes pregnancy impossible.

 The test is not required if the patient provides results of chest X-ray/fluorography/CT/MRI performed within 3 months before inclusion in the study.

 Performed in patients with positive results of the skin test (Diaskintest) or blood test for TB (QuantiFERON or T-spot).

Test	Tested variable	Frequency	Where the test is performed
		5. Day 1 of Week 134  6. Day 1 of Week 158 (only for patients from Arms 1 and 2)  7. Day 1 of Week 170 (only for Arm 3) 	
Immunogenicity assessment	• BAbs and NAbs in the serum (blood volume: 9 mL)	×8 (for Arms 1 and 2) and 9 (for Arm 3): 1. IG1 – Day 1 of Week 0, blood must be drawn before the injection of the investigational product 2. IG2 – Day 1 of Week 12 3. IG3 – Day 1 of Week 24 4. IG4 – Day 1 of Week 54 5. IG4-1 – Day 1 of Week 64  6. IG5 – Day 1 of Week 86  or Day 1 of Week 98  7. IG6 – Day 1 of Week 110  or Day 1 of Week 122  8. IG7 – Day 1 of Week 134  or Day 1 of Week 146  9. IG8 – Day 1 of Week 154  or Day 1 of Week 166 	Separate subdivision of JSC BIOCAD (central laboratory)
Tuberculosis diagnostics	• Diaskintest OR	×7: 1. At screening 2. Day 1 of Week 26 	Study center/central lab/third-

 Only for patients from Arm 3.

 Only for patients from Arms 1 and 2.

 If the patient has to take a Diaskintest, at Visit 14 he/she will receive a referral for the test. The Diaskintest must be performed within 7 days after the referral. If the TB test show uncertain/positive results, the patient should be called to the study site for an unscheduled visit where he/she will be given a referral to a TB clinic. If the TB is confirmed,

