### **Diagnostics of tuberculosis at subsequent visits**

In sufficient time in advance before Visits 14, 22, 25, 27, 29, 32, and 32-2, on which the test is planned (if Diaskintest is planned for the patient), the patient will receive a referral to Diaskintest. Diaskintest results should be obtained not earlier than 14 days before Visits 14, 22, 25, 27, 29, 32, and 32-2, respectively, where the test is to be performed. The Diaskintest must be performed within 7 days after the referral.

During the main and extension periods (at Visits 14, 22, 25, 27, 29, 32, and 32-2), if the first test for TB (QuantiFERON/T-spot/Diaskintest) is uncertain/positive, blood for the second test for TB (QuantiFERON or T-spot) should be drawn as soon as possible. A written approval from the Sponsor is not required. All patients with initial uncertain/positive tests for TB should undergo chest X-ray; if necessary, X-ray can be replaced with or supplemented by chest computed tomography (if lesions suggesting tuberculosis have been detected in this area).

If repeated tests (QuantiFERON/T-spot) give uncertain/positive results, the patient should be referred to a TB Specialist for a consultation. The TB Specialist should exclude or confirm the diagnosis of tuberculosis and decide whether the patient has contraindications to treatment with genetically engineered biological products (for diagnostics at Visits 14, 22, 25, 27, and 29).

Results of additional diagnostics (repeated QuantiFERON/T-spot test) should be interpreted in the following way:

If the test is negative, the patient can continue to participate in the study provided that chest X-ray shows no signs suggesting tuberculosis.

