#### **4.7.6.1. Skin test for tuberculosis**

Diaskintest® is a cutaneous TB test in this study. Diaskintest® is an intra-skin diagnostic test with a recombinant protein containing two antigens (ESAT6 and CFP10) of *Mycobacterium tuberculosis* and *Mycobacterium bovis*, virulent strains of mycobacteria. The procedure and results assessment of Diaskintest® are similar to those of the Mantoux test (PPD-L). The test is done with a thin needle, intradermally, into the middle third of the antebrachium. After 72 hours, the physician or nurse evaluates the response by measuring the transverse (with reference to the brachium axis) size of hyperemia and infiltrate (papula) in mm with a transparent ruler. Hyperemia is taken into account only if no infiltrate is seen. The following responses for the test can be seen (source [http://www.diaskintest.ru/page\\_2.html](http://www.diaskintest.ru/page_2.html)):

- Negative: no infiltrate or hyperemia. A “prick reaction” of up to 2 mm may occur.
- Uncertain: hyperemia with no infiltrate.
- Positive: an infiltrate (papula) of any size.

The Diaskintest® is performed at a local TB clinic or at the study site if a qualified healthcare professional is available (materials for the tests performed at study sites will be provided by JSC BIOCAD).

The Diaskintest results are valid if the test was performed within 3 months before signing the ICF. There is a high risk of false-negative results if the skin test is done more often than once in 3 months.

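### At Visit 14 (Week 26) protocol footnotes 59 and 94 and section 4.7.6 give different TB instructions: the referral dates conflict, and the repeat test, chest X-ray and continuation rules do not line up

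*Protocol*

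**What the plan says.** **Footnotes.** Footnote 59 (section 4.6.2) is called from the TB test in the Visit 14 list, although it prints below the Visit 15 list. It says of a patient due a Diaskintest that "he/she will receive a referral for the test on this Visit". Footnote 94 (Table 30) agrees: "at Visit 14 he/she will receive a referral for the test". Both allow 7 days to do the test. An uncertain or positive result brings the patient back for an unscheduled visit and a referral to a TB clinic. Confirmed TB is an adverse event and means withdrawal. Otherwise "Patients can continue the study if the TB Specialist provides a documented impression that the patient has no TB infection", and "the blood work for TB may be repeated on the discretion of the TB Specialist".

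**Section 4.7.6, subsequent visits.** This text names Visit 14 and gives the referral ahead of the visit: "Diaskintest results should be obtained not earlier than 14 days before Visits 14, 22, 25, 27, 29, 32, and 32-2". After an uncertain or positive first test, "blood for the second test for TB (QuantiFERON or T-spot) should be drawn as soon as possible", and every such patient has a chest X-ray. If repeat tests "give uncertain/positive results, the patient should be referred to a TB Specialist for a consultation". What follows depends on the repeat:

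- Negative: the patient continues if the X-ray is clear.
- Uncertain: the patient continues if the specialist reports no active TB and no contraindication to biologics.
- Positive: the same specialist finding is needed, plus a Sponsor letter.

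**X-ray rules.** The chest X-ray section (printed as 1.7.7) lists Visits 22, 25, 27, 29, 32 and 32-2 and uses a positive or uncertain trigger. Footnotes 65, 70, 74, 80, 84 and 91 say positive only. Table 25, the Visit 14 list and Table 30 show no Week 26 X-ray. The Week 54 X-ray is unconditional in Table 25, the Visit 22 list and Table 30, but conditional in the chest X-ray section.

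**The concern.** All of this is current protocol text on the same visit, and nothing ranks one part above another. Visit 14 includes a BCD-085 dose. A site working from the visit list and its footnote gives that dose before the Diaskintest result exists, may not draw a second blood sample, and finds no instruction to take an X-ray. A site working from section 4.7.6 makes the referral earlier and does both.

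Two things are at stake. One is consistent on-treatment TB surveillance for a drug whose own risk assessment (section 1.4.2) raises reactivation of latent infection. The other is the adverse-event record. Section 8.3.1 records confirmed positive TB tests as adverse events, and footnote 125 lets a retest result count where one is done. Whether a patient with a positive first test is recorded can therefore depend on whether the site drew the repeat.

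**Working it through.** There is no planned figure to reproduce. The check is a comparison of the texts and a count of days.

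| Point at Visit 14 | Footnotes 59 and 94 | Section 4.7.6 |
|---|---|---|
| Diaskintest referral | At the visit | Ahead of the visit |
| Repeat blood test | Specialist's discretion | As soon as possible after an uncertain or positive first test |
| Chest X-ray | Not mentioned | All uncertain or positive first tests |
| TB referral | Every uncertain or positive test | After an uncertain or positive repeat |
| Stated route to continue | Specialist documents absence of TB infection | Depends on the repeat; active TB is the bar |
| Call-back visit | Yes | Not mentioned |

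**Timing on the footnote route.** Inputs: 0 to 7 days from referral to test (footnotes and section 4.7.6), and section 4.7.6.1: "After 72 hours, the physician or nurse evaluates the response", which is 3 days.

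- Reading: 0 + 3 = 3 to 7 + 3 = 10 days after Visit 14, hence after the Week 26 dose.
- The next dose is at Week 30, 28 days later. The margin left is 28 − 10 = 18 to 28 − 3 = 25 days.

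**Timing on the section 4.7.6 route.** To be sure of a reading before the dose, the referral must come at least 7 + 3 = 10 days before Visit 14. For even a same-day test to be read no more than 14 days before the visit, the referral must come at most 14 + 3 = 17 days before. Visit 13 (Week 24) has no dosing in its procedure list and falls nominally 14 days before Visit 14, inside 10 to 17. A referral there is read 14 − 10 = 4 to 14 − 3 = 11 days before the dose. With the ±3-day windows in Table 25 the gap can run from 14 − 6 = 8 to 14 + 6 = 20 days, so a rule should fix the reading date and not only the referral visit.

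**X-ray.** Section 4.7.6 asks for an X-ray after an uncertain or positive first test at Visit 14, but no schedule and no visit list provides one. Table 30 now counts 6 X-rays per arm; with a conditional Week 26 entry it would be 7.

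**The case against.** The strongest reply is that only the referral date is a true contradiction. Most of that stands.

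- **Work-up.** The two texts are partly additive. The footnotes do not forbid a repeat test or an X-ray, and section 4.7.6 does not forbid early referral. A site can do all the steps. The opening of section 4.7.6 itself describes the second blood assay permissively, so some of the tension lies inside that section.
- **Continuation.** A reader might infer that a patient with latent infection would be withdrawn under the footnotes and kept under section 4.7.6. The documents do not support that. The footnotes say patients can continue if the specialist rules out infection, not only if. Their withdrawal order covers confirmed TB, and withdrawal criterion 7 (sections 4.8.2 and 5.3) requires active TB. What remains is that the footnotes give such a patient no stated route, while exclusion criterion 11 treats latent infection as a category of its own. A site could reasonably hesitate.
- **Dosing.** A reader might also infer that section 4.7.6 holds the Week 26 dose until the result is known. It does not: it sets no latest date and no dose hold, and neither text requires a blood-test result before dosing. On the footnote route the result still comes 18 to 25 days before the next dose.
- **Deferring to section 4.7.6.** It would be wrong to say that nothing is lost by this. The call-back visit and TB-clinic review of every uncertain or positive first test appear only in the footnotes.

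The reply does not remove the referral conflict, the missing X-ray entries, or the fact that a site following only the footnotes can omit steps that section 4.7.6 asks for.

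**Conclusion.** The point holds and is minor. The referral timing conflicts outright, and the footnote route puts the Diaskintest reading about 3 to 10 days after the Week 26 dose. The repeat test, X-ray and continuation rules are incomplete or inconsistent between the two places. The X-ray visit lists and triggers also disagree.

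The number of patients affected is unknown. The documents do not say how many are tested by Diaskintest rather than blood test, give no rate of uncertain results, and allow that some patients had passed Visit 14 before version 2.0 (section 4.6.1). A reader might infer about three positive first tests from the spondylitis extension, which had 2 positive Diaskintests among 81 patients over 40 weeks: 213 × 2/81 × 26/40 = 3.4. That figure assumes the same rate in psoriasis, constant over time, with all 213 patients reaching Week 26. The exact 95% interval for 2/81 (0.3% to 8.6%) alone gives 0.4 to 12.0. Counting the preceding 16-week study as well gives 213 × 2/81 × 26/56 = 2.4. The estimate is too fragile to size the problem.

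The primary endpoint is read at Week 12, before Visit 14, so it is not affected, and neither are alpha and power. Active TB leads to withdrawal under every reading.

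**What to change.** Replace the text of footnotes 59 and 94 with: *The Diaskintest referral is given at Visit 13 (Week 24), or at another time early enough, so that the result is read within the 14 days before Visit 14 and before the Week 26 dose. If the result is uncertain or positive, call the patient to an unscheduled visit and manage under section 4.7.6.*

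Then:

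- In the opening of section 4.7.6, state that the repeat blood test at on-treatment visits follows the subsequent-visits text.
- Change X-ray footnotes 65, 70, 74, 80, 84 and 91 to positive or uncertain.
- Add a conditional Week 26 X-ray to the chest X-ray section, Table 25, the Visit 14 list and Table 30 (count 6 to 7).
- Have the sponsor confirm that a negative repeat with a clear X-ray needs no TB Specialist review. Section 4.7.6 says so, but the footnotes now send those patients to a TB clinic. This is a clinical choice.
- State the Week 54 X-ray rule one way.

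The cost is protocol wording. At Visit 14 no test is added beyond those section 4.7.6 already asks for; at Week 54 the number of X-rays depends on which existing rule is kept. Because TB management is touched, the change may need approval as a non-administrative amendment under section 12.1. No analysis changes.

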**Procedures of Visit 16 (Day 1 of Week 34)**

- Complete blood count [REDACTED]
- Blood chemistry [REDACTED]
- Physical examination.
- Administration of BCD-085.
- Blood pressure, heart rate and body temperature (immediately after dosing).
- Information about concomitant therapy.
- Assessing injection site reactions.
- Recording AEs/SAEs.

[REDACTED]

**Procedures of Visit 17 (Day 1 of Week 38)**

- Physical examination.
- Administration of BCD-085.
- Blood pressure, heart rate and body temperature (immediately after dosing).
- Information about concomitant therapy.
- Assessing injection site reactions.
- Recording AEs/SAEs.

**Procedures of Visit 18 (Day 1 of Week 42)**

- Physical examination.
- Psoriasis Area and Severity Index (PASI), including Body Surface Area affected by psoriasis (BSA).
- Static Physician's Global Assessment (sPGA).
- [REDACTED]
- DLQI questionnaire.
- Complete blood count [REDACTED]
- Blood chemistry [REDACTED]
- Administration of BCD-085.
- Blood pressure, heart rate and body temperature (immediately after dosing).
- Information about concomitant therapy.

- Assessing injection site reactions.
- Recording AEs/SAEs.

Total blood volume drawn at the visit: 12.5 mL.

### **Procedures of Visit 19 (Day 1 of Week 46)**

- Physical examination.
- Administration of BCD-085.
- Blood pressure, heart rate and body temperature (immediately after dosing).
- Information about concomitant therapy.
- Assessing injection site reactions.
- Recording AEs/SAEs.

### **Procedures of Visit 20 (Day 1 of Week 50)**

- Physical examination.
- Administration of BCD-085.
- Blood pressure, heart rate and body temperature (immediately after dosing).
- Information about concomitant therapy.
- Assessing injection site reactions.
- Recording AEs/SAEs.

